6.1.4. Safety Measures: Survey of Autonomic Symptoms (SAS) Scores

The following non-standard safety tables will be included:

- Summary of the Survey of Autonomic Symptoms (SAS) number of symptoms reported and total symptom impact score as continuous data, at each visit, and for the change from Screening score (scores defined in [Section 3.5.4](#) above).

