NSAID (outside of oral investigational product) limit compliance					X	X	X	X	X	X	X	X	X
Remind subject of contraceptive requirements	X			X	X	X	X	X	X	X	X	X	X
Laboratory													
Hepatitis Screen (Hepatitis B & C); HIV, Urine Toxicology screen	X												
Hemoglobin A1c	X												
Serum FSH testing ⁱ	X												
Serum/Urine Pregnancy Test ⁱ	X			X			X		X	X	X		X
Hematology	X			X					X				
Blood Chemistry	X			X					X				
Urinalysis	X												
Serum/Plasma Retention Sample				X					X				X
Plasma Pharmacokinetic sample ^k				X	X	X	X		X		X ^l		X
Serum Pharmacodynamic sample (NGF) ^k				X	X	X	X				X ^l		X
Serum Anti-Drug Antibody ^k				X			X		X		X ^l		X
Serum and urine biomarkers ^m				X									
Banked biospecimen (whole blood)				X									

Visit Identifiers	Screen			Treatment Period									
	SC. Stage 1	SC. Stage 2	IPAP	Baseline ^a	Week 2	Week 4	Week 8 ^a	Week 12 ^b	Week 16 ^a	Week 24 ^a	Weeks 32, 40, 48 ^a	Weeks 20, 28, 36, 44, 52 ^b	Week 56/ End of Treatment
Study Activities	Day - 37 to -5		Day-5 to -1	Day 1 Dosing Visit	Day 15 (±2 days)	Day 29 (±3 days)	Day 57 (±7 days) Dosing Visit	(±7 days) Telephone Contact	Day 113 (±7 days) Dosing Visit	(±7 days) Dosing Visit	(±7 days) Dosing Visits	(±7 days) Telephone Contact	Day 393 (±7 days)
Trial Treatment													
Pre-study Celecoxib Dispensed/Regimen Stabilization	X	At least 2 or 3 weeks prior to Baseline (Day 1) visit ⁿ											
Assess treatment response and eligibility to continue in the trial ^o									X ^o				
Randomization				X									
SC investigational product ^p				X			X		X	X	X		
Blinded Celecoxib (Oral investigational product)				-----X-----									
Dispense Blinded Celecoxib (Oral investigational product)				X	X	X	X		X	X	X		
Dispense rescue medication	X			X	X	X	X		X	X	X		X

Table 2. Schedule of Activities: Follow-up Period

Visit Identifiers	Follow-up Period				Early Termination (ET) Procedure				
	Week 60	Week 64	Week 68, 72, 76	Week 80 End of Study	ET Visit 1	ET Telephone Contact 1	ET Visit 2	ET Telephone Contact 2	ET Visit 3
Study Activities	(±7 days) Telephone Contact	Day 449 (±7 days)	(±7 days) Telephone Contact	Day 560 (±7 days)	8 weeks after last dose of SC Study Med (±7 days)	12 weeks after last dose of SC Study Med (±7 days)	16 Weeks after last dose of SC Study Med (±7 days)	20 weeks after last dose of SC Study Med (±7 days)	24 Weeks after last dose of SC Study Med (±7 days)
Vital Signs (sitting BP, HR)		X		X	X		X		X

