3. STUDY DESIGN

Figure 5. Study Schematic

This is a randomized, double-blind, active-controlled, multicenter, parallel-group Phase 3 study of the safety and efficacy of tanezumab when administered by SC injection for up to 56 weeks in subjects with chronic low back pain. Subjects will be randomized to 1 of 3 treatment groups in a 1:1:1 ratio. Treatment groups will include:

1. Placebo SC matching tanezumab administered at an 8-week interval (total of 7 times) plus celecoxib 100 mg BID to be administered orally for 56 weeks.
2. Tanezumab 5 mg SC administered at an 8-week interval (total of 7 times) plus placebo matching celecoxib to be administered orally BID for 56 weeks.
3. Tanezumab 10 mg SC administered at an 8-week interval (total of 7 times) plus placebo matching celecoxib to be administered orally BID for 56 weeks.

The study is designed with a total duration (post-randomization) of up to 80 weeks and will consist of three periods: Screening (up to 37 days; includes a Washout Period and an Initial Pain Assessment Period [IPAP]), Double-blind Treatment (56 weeks) and Follow-up (24

weeks). The Screening Period (beginning up to 37 days prior to Randomization) includes a Washout Period (lasting 2-32 days), if required, and an IPAP (the 5 days prior to Randomization/Baseline).

Prior to entering the study, subjects must be experiencing some benefit (eg, analgesic effect) from their current stable dose regimen of oral therapy of NSAID (celecoxib 200 mg/day [100 mg BID], loxoprofen 120 to 180 mg/day or meloxicam 5 to 15 mg/day) treatment, be tolerating their NSAID regimen, be taking this medication regularly (defined as an average of at least 5 days per week) during the 30 day period prior to the Screening Visit.

At the Week 16 visit, subjects must have at least a 30% reduction in weekly average LBPI score relative to Baseline and at least a 15% reduction in weekly average LBPI score relative to Baseline at any week from Week 1 to Week 15 in order to continue investigational product. Subjects who do not meet these response criteria will be discontinued from the Treatment Period and enter the 24-week Early Termination Follow-up Period (See Section 6.9.1).

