7.3.7. Survey of Autonomic Symptoms (SAS)

The Survey of Autonomic Symptoms (SAS) is a validated, easily administered instrument to measure autonomic symptoms that has been proposed to be valuable in assessing neuropathic autonomic symptoms in clinical trials (refer to [Appendix 15](#)).

Subjects will complete the SAS at Screening, prior to SC dosing at Weeks 24, 56 and 80 (or at Early Termination Visits 1 and 3). Subjects will enter responses in IRT.

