9.1. Sample Size Determination

In terms of the study feasibility and the safety evaluation described below, the total sample size will be approximately 200 subjects (170-220 subjects, approximately 66 subjects [56-73 subjects] per treatment group). However, it is acceptable to randomize more than 220 subjects from the safety perspective as described below because primary objective is to evaluate the long-term safety.

Japanese subjects are enrolled in two studies within the tanezumab CLBP program (A4091059 and this study). In ongoing A4091059 study (randomization was finished in June 2017), 129 Japanese subjects were randomized and appropriately 57 Japanese CLBP subjects are expected to be initially randomized to the tanezumab arm. Considering approximately 133 (113-146) subjects are expected to be randomized to the tanezumab arm in this study, the safety data will be collected from approximately 190 (170-203) Japanese CLBP subjects treated with tanezumab.

The primary objective of this study is the evaluation of long term safety. The number of subjects who complete this study is estimated as described below. Both these protocols

require subjects to meet the efficacy response criteria (defined as at least a 30% reduction in weekly average LBPI score at week 16 relative to Baseline and at least a 15% reduction in weekly average LBPI score from Baseline at any week from week 1 to week 15) at week 16 in order to continue in the study. The proportion of 30% responders at week 16 was approximately 60% in two OA phase 3 studies (A4091011, A4091014) and approximately 42% in one CLBP phase 3 study (A4091012). On the other hand, the proportion of subjects discontinuing after week 16 is assumed to be approximately 10% for OA and approximately 20% for CLBP based on the results of discontinuation for reasons other than insufficient clinical response in these studies.

Therefore, the proportion of subjects expected to complete this study was calculated as approximately 54% ($=100*0.6*0.9$) based on the two OA studies and approximately 34% ($=100*0.42*0.8$) based on the CLBP study, and the proportion of completers of this study is estimated to be between 34% and 54%. Table 6 shows the relationship between the proportion of completers and the number of subjects with one year exposure.

From Table 6, if the proportion of completers is at least 43% in the CLBP program, approaching 100 subjects are expected to be treated with tanezumab for a minimum of one year.

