3. ENDPOINTS AND BASELINE VARIABLES: DEFINITIONS AND CONVENTIONS

3.1. Primary Endpoints

Safety Measures

- *Adverse events.*
- *Standard safety assessments (safety laboratory testing [chemistry, and hematology], vital signs).*
- *Orthostatic (supine/standing) blood pressure assessments.*
- *Survey of Autonomic Symptoms (SAS) scores.*
- *Electrocardiogram (ECG, 12-lead) assessments.*
- *Joint Safety adjudication outcomes.*
- *Total joint replacements.*
- *Neurologic examination (Neuropathy Impairment Score [NIS]).*
- *Anti-drug antibody assessments (ADA).*
- *Physical examinations.*
- *Outcome of Consultation*

The details of the safety endpoints are described in [Section 3.5](#).

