6.1.7. Safety Measures: Neurologic Examination (Neuropathy Impairment Score [NIS])

The change from Baseline in the NIS for Weeks 2, 4, 8, 16, 24, 32, 40, 48, 56, 64 and 80 will be summarized. The number and percentage of subjects whose NIS score worsened (change>0), improved (change<0) or had no change will also be shown. Missing data will be imputed using LOCF only. For this analysis, Baseline data will not be carried forward in the case of a post-Baseline observation not being available for use in LOCF. An additional analysis will use the change from Baseline to the largest (worst) post-Baseline value and to the last post baseline value. The last post baseline value will only be used in the summary of change from baseline (not be used in the summary with change categories).

Neurological-related safety data

The “conclusion from the neurological examination” data will be summarized for each timepoint and the final assessment over all neurological examinations for each subject. In addition the persistence of any neurological examination finding will be summarized, showing the incidence of subjects with new or worsened neurological examination abnormality (both clinically significant only and also for any finding) for 2, 3, 4, and ≥ 5 consecutive visits.

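### The Survey of Autonomic Symptoms is first scheduled on treatment at Week 24, after the Week 16 response rule, and SAP 6.1.4 has no summary that combines early stoppers with continuing subjects

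*SAP*

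**What the plan says.** SAP 3.1 lists "Survey of Autonomic Symptoms (SAS) scores" among the primary endpoints, all of which are safety measures.

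Protocol 7.3.7 gives the schedule: "Subjects will complete the SAS at Screening, prior to SC dosing at Weeks 24, 56 and 80 (or at Early Termination Visits 1 and 3". Protocol Table 2 times ET Visit 1 at "8 weeks after last dose of SC Study Med (±7 days" and ET Visit 3 at "24 Weeks after last dose of SC Study Med (±7 days".

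The Week 16 rule in Protocol 3 requires a set reduction in pain score. "Subjects who do not meet these response criteria will be discontinued from the Treatment Period and enter the 24-week Early Termination Follow-up Period".

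The SAS analysis in SAP 6.1.4 summarises the "number of symptoms reported and total symptom impact score as continuous data, at each visit, and for the change from Screening score". SAP 5.3 makes observed data without imputation the default where nothing else is specified.

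Other repeated safety measures get more. For the Neuropathy Impairment Score (NIS), SAP 6.1.7 adds LOCF and a further step: "An additional analysis will use the change from Baseline to the largest (worst) post-Baseline value and to the last post baseline value". SAP 3.5.3 summarises orthostatic hypotension by visit, at the last visit and at any time after baseline. SAP 6.1.2 summarises sitting blood pressure by maximum increase, maximum decrease and change to last observation.

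**The concern.** A subject must pass a pain-response test before reaching the first scheduled on-treatment SAS. Those who fail it do complete the SAS, but at visits timed from their last dose. A table organised by scheduled visit therefore shows continuing subjects in its Week 24, 56 and 80 rows. Early stoppers appear, if at all, in rows of their own, and no planned row represents the treated arm.

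This matters because the primary objective is long-term safety. Passing the Week 16 rule is a post-randomisation outcome that may differ between tanezumab and celecoxib. A reader setting the arms side by side at Week 24 or later would be looking at groups filtered on pain response, not at the groups as randomised. The SAS asks every subject about the same listed symptoms and how much they bother them, which spontaneous or elicited adverse event reports do not replicate.

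**Working it through.** **Inputs**
- 30% responders at Week 16, Protocol 9.1: "The proportion of 30% responders at week 16 was approximately 60% in two OA phase 3 studies (A4091011, A4091014"), and about 42% in the chronic low back pain study.
- Discontinuation after Week 16, Protocol 9.1: about 10% (osteoarthritis) and 20% (low back pain).
- Planned size, Protocol 9.1: about 66 per arm, about 133 on tanezumab, about 200 in all.
- Doses at Day 1, Week 8 (Day 57), Week 16 (Day 113) and every 8 weeks to Week 48 (Day 337).

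**Step 1. Reproduce the protocol's completion estimate**

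Completers = responders × (1 − later discontinuation).
- Osteoarthritis: 0.60 × 0.90 = 54%.
- Low back pain: 0.42 × 0.80 = 33.6%, stated as 34%.

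Both agree with Protocol 9.1.

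**Step 2. When non-responders complete the SAS**

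A subject who fails the Week 16 rule was last dosed on Day 57.
- ET Visit 1: 57 + 56 = Day 113, about Week 16.
- ET Visit 3: 57 + 168 = Day 225, about Week 32.

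Neither is a scheduled SAS week.

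**Step 3. Share missing from each scheduled summary, if ET records are not windowed in**

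| Summary | Formula | 60% responders | 42% responders |
|---|---|---|---|
| Week 24, Week 16 failures only | 1 − responders | 40% | 58% |
| Week 56, and at least this at Week 80 | 1 − completers | 46% | 66% |

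- Week 24, per arm of 66: 66 × 0.40 = 26 to 66 × 0.58 = 38 missing. Over all arms: 200 × 0.40 = 80 to 200 × 0.58 = 116. On tanezumab: 133 × 0.40 = 53 to 133 × 0.58 = 77.
- Week 56, per arm of 66: 66 × 0.46 = 30 to 66 × 0.664 = 44 missing, so 36 down to 22 remain.

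**Step 4. Is there a rule that places ET records?**

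The windows in SAP Appendix 2.1 allocate efficacy observations, and none is given for the SAS. Two readings by analogy:
- General visit windows: Day 113 falls in Week 16 [86, 141] and Day 225 in Week 32 [198, 253], not in Week 24 [142, 197].
- Wide windows, as for EQ-5D-5L, where Week 16 is [2, 253]. That upper limit is the midpoint of the two target days: (113 + 393)/2 = 253. The same construction for the SAS would end Week 24 at (169 + 393)/2 = 281, so both ET records would fall in it.

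Some ET visits coincide with a scheduled week in any case. A subject dosed only on Day 1 has ET Visit 3 at Week 24, and one last dosed at Week 32 has it at 32 + 24 = Week 56. The contents of each row depend on a rule the SAP does not state.

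**Step 5. A common anchor**

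Week 56 is Day 393, and 393 − 337 = 56 days after the last dose. ET Visit 1 is also 8 weeks after the last dose. The two are therefore equally spaced from dosing for completers and early stoppers.

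**The case against.** The strongest reply is that the omission is not written in the plan. ET Visits 1 and 3 are named SAS visits, so a summary by visit could show them as rows, and the SAP uses wide windows for sparsely collected instruments. Under Protocol 6.9, subjects who refuse ET follow-up have one visit that includes the Week 80 procedures, hence the SAS. This stands: a reader might infer that early stoppers' scores are not collected, or are certain to be left out, and the documents support neither. But separate ET rows would hold only early stoppers, so the absence of a combined summary remains.

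Second, SAP 5.1 tests no hypotheses and SAP 6.1.4 plans no between-arm SAS estimate. A reader might infer that a planned comparison is biased; there is none. What is affected is the interpretation of descriptive columns by arm.

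Third, autonomic safety in early stoppers is examined elsewhere. SAP 6.1.1 gives risk differences for the combined Tier-1 events, tables of sympathetic nervous system events, and adverse event summaries over the whole study. Orthostatic hypotension at any post-baseline time and the outcome of sympathetic neuropathy assessment are also summarised. It would be wrong to say that autonomic symptoms in early stoppers go unanalysed.

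Fourth, the SAS is not the only primary measure without an all-subject assessment by Week 16. The scheduled X-rays follow the same weeks (Protocol 7.3.8), and the general physical examination is at Screening and Week 56 or ET Visit 1 (Protocol 7.3.1.1).

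Finally, a summary to the last post-dose value, as for the NIS, would not serve well. With full follow-up, last means ET Visit 3 (24 weeks after dosing) or Week 80 (80 − 48 = 32 weeks). At the 17 to 24 day half-life in Protocol 1.2.4.6.1, 24 weeks is 168/24 = 7 to 168/17 = about 10 half-lives. That objection is accepted, and the fix uses an end-of-treatment anchor instead.

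**Conclusion.** The point holds as a gap in the SAS analysis. The first on-treatment post-dose SAS comes after the Week 16 rule, the handling of ET records is unstated, and no planned summary combines early stoppers with continuing subjects, although the SAP does this for the NIS, orthostatic hypotension and sitting blood pressure.

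On the protocol's own assumptions, about 40-58% of each arm would be absent at Week 24, and about 46-66% at Week 56 and at least that at Week 80, unless ET records are windowed in.

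These ranges rest on response rates from earlier studies applied equally to all three arms. They leave out the additional 15% response criterion, and the protocol does not say how dropouts before Week 16 were counted. The Week 24 range counts Week 16 failures alone, so other early losses would add to it. A difference in selection between arms is possible, but the documents do not allow it to be sized.

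**What to change.** Add to SAP 6.1.4, by arm and over all treated subjects with a post-dose SAS, the change from Screening in number of symptoms and in total impact score:
- (a) to the end-of-treatment SAS, meaning Week 56, or ET Visit 1 if treatment stopped early;
- (b) to the worst post-dose value, including ET Visits 1 and 3, as support.

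State how ET records are assigned, including the single visit of subjects who refuse ET follow-up. Keep the by-visit table. With ET records in their own rows, footnote that Weeks 24, 56 and 80 contain only subjects who continued past the Week 16 rule.

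The cost is a few sentences and one table from data already collected. The limits should be stated with it:
- Subjects contribute unequal numbers of records to the worst value, so it depends partly on retention.
- Time on treatment differs at the end-of-treatment value.
- The SAS asks about the past six months (about 26 weeks), so an ET Visit 1 near Week 16 reaches back about 26 − 16 = 10 weeks before dosing.
- The documents give no ET attendance rate, so the coverage gained cannot be quantified.

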6.1.5. Safety Measures: Electrocardiogram (ECG, 12-lead) Assessments

Pfizer standard safety data presentations will be made for ECG data such as PR, QRS, QT, QTcF, QTcB, RR intervals, and heart rate [HR].

6.1.6. Safety Measures: Joint Safety Adjudication Outcomes and Total Joint Replacements

Adjudication outcomes to be summarized include rapidly progressive osteoarthritis (type-1 only), rapidly progressive osteoarthritis (type-2 only), rapidly progressive osteoarthritis (type-1 or type-2 combined), subchondral insufficiency fracture, primary osteonecrosis, pathological fracture, normal progression of OA and other joint outcomes. The incidence of subjects with any of the adjudication outcomes of rapidly progressive osteoarthritis (type-1 or type-2), subchondral insufficiency fracture, primary osteonecrosis, or pathological fracture will also be summarized. Total joint replacement (TJR) will also be summarized. Output will show the number and percentage with 95% CI (exact confidence interval) of subjects for each outcome. In addition, subject years of exposure for individual treatment group and exposure adjusted event rates (number of subjects with an adjudicated joint safety event divided by exposure) of each outcome (with 95% CI) will also be shown. For each outcome, association with TJR, affected joint(s), and baseline Kellgren-Lawrence Grade of affected joint will be summarized. Number of TJRs during study, study period of first TJR occurrence, number of only elective TJR, number of joints with TJR prior to study, location of TJR prior to study will also be summarized.

Events will be included in summaries if they occur up to the end of the safety follow-up period or 26 weeks (planned duration of the follow-up period + 2 weeks) after the end of the treatment period, whichever is later.

For the joint safety event analyses, the observation period is defined as the time from first SC dose to study completion or discontinuation for subjects who did not have an event, or time from first SC dose to the earliest event for subjects who did have at least one event.

Reporting of total joint replacement events including surgery will be described in a separate Statistical Analysis Plan that will cover patients in this subset from Studies 1059, 1061 and 1063. Corresponding data from Studies 1056, 1057 and 1058 will be reported under study 1064. Summary listings for the data from the 1063 substudy will be part of the 1063 study CSR as there are <10 total joint replacement events expected in the substudy.

